Specific Aim 1: Compare the effectiveness of an evidence-based HIV risk reduction intervention (MI-HIV) to HIV Education (NIDA Standard) in reducing sex risk behaviors, injection practices, and drug use among a culturally unique sample of disadvantaged, drug-using rural women at high-risk for HIV and HCV. This aim will be accomplished through the random selection of high-risk rural women drug users from rural jails, screening and assessment for high-risk behavior, and random assignment to the HIV-Education or MI-HIV intervention conditions. Follow-up interviews at 3, 6, and 12 months in the community post-release will examine changes in high-risk behavior. It is expected that MI-HIV participants will report significantly greater reductions in risky injection drug use practices, other drug use, and sex risk behaviors than women who participate in the HIV-Education condition.

Specific Aim 2: Examine MI-HIV Intervention engagement as a predictor of community health and behavioral health service utilization (including drug treatment and mental health) at follow-up among disadvantaged, drug-using rural women at high risk for HIV and HCV. This aim will focus on community service utilization during the follow-up period by the intervention and education comparison group, and how health and behavioral health service utilization relates to patterns of HIV/HCV risk behavior. It is expected that MI-HIV participants will utilize more services due to increased motivation for treatment and treatment planning following the brief intervention.

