(2) Motivational Interviewing-based HIV Risk Reduction (MI-HIV, n=175): In this condition, women will also participate in the NIDA Standard HIV intervention during the pre-test counseling session and complete their HIV/HCV testing session. In addition, they will participate in brief intervention sessions which target motivation to change their injection drug use practices, other drug use, and risky sex behaviors. A minimum of four brief intervention sessions (maximum of 12 sessions) will be conducted over a 12 week (3 month) study period between baseline and the first 3 month follow-up (two sessions within 1 week prior to release from jail and two sessions by phone during the first 30 days and 60 days in the community) which is consistent with the overall approach (Weir, 2009). The summary of intervention sessions is found in Table 1. Participants will be randomized to MI-HIV with at least 2 weeks left to serve in jail so that enough time is allotted to complete the jail-based sessions. The study interventionist (hired from the local area and familiar with local resources) will meet face-to-face with participants for two brief intervention sessions prior to their release. As noted in the support letters, each jailer has agreed to provide confidential space within the jail for private therapy sessions.

Table 1. Summary of MI-HIV Sessions

Study Session	Location	Time Frame	MI-HIV Core Component	Content
Session 1	Jail	Within 2 week of randomization	MI-HIV Component 1	to identify risky sexual behavior and risky drug use (including needle use) using an assessment tool (NIDA RBA/Woman)
Session 1 – 2	Jail	Within 2 week of randomization	MI-HIV Component 2	to discuss with the woman her perception of the risks associated with those behaviors
Session 1 – 12	Jail	Within 2 week of randomization	MI-HIV Component 3	to determine her readiness to address those risks
Follow-up	Community/Phone	30 days post-release	MI-HIV Component 4	to engage in stage-base discussion about behavior change
Follow-up	Community/Phone	60 days post-release	MI-HIV Component 4	to engage in stage-base discussion about behavior change

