13. **Research Materials, Records, and Privacy:** Self-reported behavioral data will be collected at the baseline and at 3, 6, and 12 months post-release from jail for follow-up interviews, along with HIV/HCV Orasure tests. The study interviewer will attend an intensive week-long training that covers topics including human subjects protection and issues that could arise during jail-based data collection. For example, training will be conducted on the importance of ensuring that all materials brought in to the jail are also taken out of the jail by the interviewers (e.g., pens, study materials, etc). A variety of behavioral data including demographic characteristics, past drug use, injection drug use, health and mental health problems, and service utilization will be collected through self-reports using Computer Assisted Personal Interviewing. administration with a portable computer (DELL notebook). During the CAPI portion of the interview, the trained interviewer will read the instructions, questions, and response categories from a laptop and directly enter the participant's response. The CAPI formatting will be programmed using Questionnaire Development System (QDS™) from Nova Research (<http://www.novaresearch.com>). Data with the participant ID and all other identifying information (consent form, locator sheet, payment forms) will be stored separately. Consent forms, locator sheets, and payment forms will be managed on site. Security of the data will be maintained through regular computer server backups and CD Rom back-ups secured in fire-safe locked boxes. In addition, data will be collected in brief intervention sessions with the study therapist on engagement, participation, number of services attended, session content, and needed service referrals. Measures of adherence to the MI-HIV intervention will also be collected. No clinical data (including missed sessions) will be provided to jail officials or any other criminal justice official. Participation in this study will not be considered in probation or parole decisions.
14. **Confidentiality:** Every effort will be made in the protection of human participants and issues relating to participant confidentiality. Because this study will involve individuals who are incarcerated, this study's human participants' protocol will comply fully with the special protections pertaining to behavioral research involving prisoners as participants.

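### Aim 2 names engagement with MI-HIV, a post-randomization measure that exists in one arm only, as its predictor, while its hypothesis is a comparison between randomized arms

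*Protocol*

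**What the plan says.** Specific Aim 2 (Protocol, Objectives) has three sentences, and they do not name the same contrast.

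- The lead sentence gives the predictor: "Examine MI-HIV Intervention engagement as a predictor of community health and behavioral health service utilization".
- The second gives the scope: the aim concerns "community service utilization during the follow-up period by the intervention and education comparison group", and how service use relates to risk behavior.
- The third gives the hypothesis: "It is expected that MI-HIV participants will utilize more services due to increased motivation for treatment and treatment planning following the brief intervention".

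Section 13 (Research Materials, Records, and Privacy) shows where engagement is measured: "data will be collected in brief intervention sessions with the study therapist on engagement, participation, number of services attended". Only the MI-HIV arm has these sessions (Study Design; section 7), and they follow randomization, which takes place after the baseline interview. The planned minimum is four sessions, including "two sessions by phone during the first 30 days and 60 days in the community".

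The outcome is available in both arms. Section 13 states that "service utilization will be collected through self-reports using Computer Assisted Personal Interviewing", and the Study Design section schedules follow-up interviews at 3, 6 and 12 months after release.

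**The concern.** The hypothesis is about arms, but the stated predictor is a behavior within one arm. Randomization protects only the first. Engagement may differ between women because of the jail time available, whether they can be reached by phone after release and, plausibly, their motivation. Motivation is also the route by which Aim 2 expects service use to rise, so it is a natural common cause of engagement and outcome.

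If the aim is analyzed as its lead sentence reads, a positive result could be reported as support for the hypothesis although MI-HIV had done nothing. Increasing service use is one of the project's overall aims (Background), so this is not a minor endpoint.

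**Working it through.** **1. The passages side by side.**

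| Question | Lead sentence of Aim 2 | Hypothesis of Aim 2 |
|---|---|---|
| Explanatory variable | Engagement with MI-HIV | Being in MI-HIV |
| When fixed | During the sessions, after randomization | At randomization |
| Defined for HIV-Education women? | No, they have no brief sessions | Yes |
| Protected by randomization? | No | Yes |

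Aim 1 is worded differently: it sets out to compare MI-HIV with HIV Education, cites random assignment and names the comparator in its hypothesis. Aim 2 does not tie its hypothesis to random assignment, and no section says that the arm comparison tests it.

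**2. Timing.** The phone sessions at 30 and 60 days after release come before the 3-month interview. If that interview covers the time since release (the protocol states no recall period), some engagement can follow the service use it is meant to predict. The 6- and 12-month interviews come after all planned sessions.

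**3. Illustration with no true effect.** The protocol gives no service-use rate, effect size or engagement rate for this aim, so there is no plan figure to reproduce beyond 175 + 175 = 350. Everything below except the 175 per arm is assumed.

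- Motivation M ~ N(0, 1) in every woman.
- Service use in both arms: logit P = −0.4 + bM, with b = 0.5 or 1.1. Assignment has no effect.
- An MI-HIV woman is engaged if rM + √(1 − r²)·e > 0, with e ~ N(0, 1). About half are engaged (87 v 88), and r is the correlation of motivation with the tendency to engage.
- Two-sided 5% two-proportion z test, 40,000 simulated trials of 350 women per setting.

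Rejection rates (b = 0.5 / b = 1.1):

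| r | Engaged v not engaged, within MI-HIV | Engaged MI-HIV v all 175 education women | Arm v arm, 175 v 175 |
|---|---|---|---|
| 0.2 | 7.9% / 15.3% | 5.8% / 8.6% | about 5% |
| 0.3 | 11.5% / 28.5% | 7.4% / 12.7% | about 5% |
| 0.5 | 23.4% / 65.8% | 11.2% / 27.3% | about 5% |
| 0.7 | 40.6% / 91.8% | 17.0% / 48.5% | about 5% |

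At r = 0 the within-arm test also holds its 5%.

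**4. Check of one cell by formula (r = 0.5, b = 1.1).** Integrating over M gives service use of 50.8% in engaged and 33.3% in non-engaged women: a gap of 17.5 points, odds ratio 2.06, with no true effect.

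- Pooled proportion about 0.42; null standard error √[0.42 × 0.58 × (1/87 + 1/88)] = 0.0746, so the critical difference is 1.96 × 0.0746 = 0.146.
- Standard error under these proportions: √(0.508 × 0.492/87 + 0.333 × 0.667/88) = 0.0735.
- Rejection probability about Φ[(0.175 − 0.146)/0.0735] = Φ(0.39) = 65%, in line with the simulated 65.8%.

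**5. A second, simpler model.** Suppose half of the MI-HIV arm is more motivated.

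- *Strong confounding:* engagement 80% v 30%, service use 45% v 15%. Share engaged = 0.5 × 0.8 + 0.5 × 0.3 = 0.55. Motivated share among the engaged = 0.40/0.55 = 0.727; among the rest = 0.10/0.45 = 0.222. Service use = 0.727 × 45% + 0.273 × 15% = 36.8% against 0.222 × 45% + 0.778 × 15% = 21.7%: a spurious gap of 15.2 points before rounding, found significant about 59% of the time.
- *Weak confounding:* engagement 60% v 40%, service use 35% v 25%. The gap is 31% − 29% = 2 points.

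The expected difference between arms is zero in both.

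**The case against.** The best defense is that the randomized comparison is already in Aim 2. The second sentence calls the education arm a comparison group, the third states a directional expectation for MI-HIV participants, and service use is collected in both arms. The lead sentence may use engagement loosely, to mean taking part in MI-HIV; the protocol uses the word loosely elsewhere. The formal test of a secondary hypothesis usually belongs in the statistical analysis plan, which is not at hand. Examining a predictor is associational language, and no section proposes an unadjusted test of engaged against non-engaged women as proof of an effect.

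Part of this stands. The arm comparison is possible and hinted at, the protocol fixes no model, and the rejection rates are illustrative. Eligibility (willingness to take part, at least two weeks in jail) narrows the differences in engagement. The timing overlap touches only early service use.

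The rest does not remove the point. Section 13 lists engagement as session data, separately from participation, which weighs against the loose reading; if that reading was meant, the sentence needs the same correction. Nor is this a detail deferred to an analysis plan: the protocol states a predictor, and it is not one that can test the hypothesis stated two sentences later.

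**Conclusion.** The concern holds, as a mismatch between the stated predictor and the stated hypothesis; no data are missing. That conclusion rests on the text alone.

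The direction of the risk also holds: any shared cause that raises both engagement and service use produces an association without an intervention effect. Its size is an assumption. Over the slopes examined, the false-positive rate of a nominal 5% within-arm test runs from 8–15% at a correlation of 0.2 to 41–92% at 0.7. The protocol supports no particular correlation, slope or split, and the tests shown are unadjusted. The correction is worth making because it costs little and service use is among the project's overall aims.

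**What to change.** Reword Aim 2 so that its hypothesis is tested by assigned arm, MI-HIV against HIV-Education, in all randomized women, using service use from the 3-, 6- and 12-month interviews. State engagement as a separate exploratory association within MI-HIV, without causal interpretation, and say that it means the session measure in section 13.

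The cost is wording only, with no new data. The one loss is that engagement no longer leads the aim.

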6. **Informed Consent Process:** Potential participants who are interested in the study will be asked to participate in the screening session at the jail with the UK research coordinator. Potential participants will be provided with informed consent prior to the collection of screener data. As part of the informed consent process, potential participants will be assured that: (a) Neither participation nor refusal to participate in a protocol will affect their legal parole status (if applicable); (b) No individual or identifiable data collected as part of a study protocol will be made available to any criminal justice authority including jail, parole, or community mandated treatment; and (c) If potential participants do NOT wish to participate, their parole or other legal status will not be affected. Potential participants who choose NOT to participate in the study protocol will not be identified in their records, and non-participation will NOT become a matter of official record in any file. Informed consent procedures will cover participation in the screener, baseline interview, HIV/HCV testing, and follow-up interviews so that participants are fully aware of all possible study procedures before making a decision about entering the study.

Due to the sensitive nature of some of the questions asked in the interviews, confidentiality issues will be stressed during informed consent which will include a description of a federal Certificate of Confidentiality which provides an additional layer of human subject protection. Participants will also be assured that their screening results, study participation, and study data will not be made available to any representative of the criminal justice system. The research coordinator will keep detailed records on the number of interested participants who participate in the screening session and the number of refusals. Screening data will be examined as part of the implementation phase to examine characteristics of participants who enter the study compared to those who are not eligible.

Because of the short time frame between baseline and follow-up interviews (3 months), consent procedures will not be repeated at each follow-up interview since no new procedures will be introduced. However, a follow-up script will be reviewed with the participant to remind her of the key elements of informed consent.

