HIV/HCV Testing: After the NIDA Standard pre-test counseling session, HIV and HCV testing will be conducted using OraQUICK *ADVANCE*[®] Rapid HIV-1/2 and OraQUICK *ADVANCE*[®] Rapid HCV Antibody Test kits, a relatively new test with demonstrated sensitivity and specificity in clinical performance equivalent to current laboratory-based EIA (Lee et al., 2010; Lee et al., 2011), following procedures used in other NIDA-funded studies (Havens et al., R01 DA024598; Oser et al., R01 DA022967). Pre-and post-test counseling, following CDC protocols, will be conducted at the baseline, 6-month, and 12-month interviews. Pre-test counseling will occur following the testing procedures with respondents told about the purposes and procedures of testing, test results meaning, and confidentiality. Post-test counseling will be conducted by the research staff, who will be certified HIV/HCV counselors. At post-test counseling, respondents are told the results of their tests and are assured that the results will remain confidential. Regardless of test results, all respondents will remain in the research study. Moreover,

they will be told what a positive test result means, and, if the respondent wishes, referrals will be made to appropriate agencies for continuing treatment and other health assistance, crisis intervention, and support. Participants will also be given information about the services provided by each local health department regarding HIV/HCV resources. Women testing positive in the jail will be referred to the medical staff at the jail for additional services, but it is their option to follow through on services during their incarceration. Women testing positive who do not wish to engage in health care services within the correctional setting will be offered referrals to community-based services once released, including a referral to the Bluegrass Care Clinic, the clinic of the University of Kentucky Medical Center specializing in HIV primary care.

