9. **Potential Risks:** The procedures to be used by this study will involve conventional clinical and social science research methods that are routine in studies of this type. The potential psychological risks will be discussed with participants during recruitment contacts to assist them in making an informed decision as to whether they wish to participate in a study protocol. These potential psychological risks are primarily related to being asked questions in the interview that they do not feel comfortable asking. There is also a risk that for participants assigned to the MI-HIV condition, there may be a breach of confidentiality of their study files or counseling information. Every effort will be taken to ensure that this does not happen. Therapist records for client sessions will be completed and stored in the research office at UK. No files – hard copy or electronic – will be stored in the jail. For participants who are not randomized in to the MI-HIV condition that they may have to wait to get in to treatment services in the community. These risks will be discussed with each potential study participant during the informed consent process.
- Screening for substance use with a criminal justice involved sample can be biased by a participant's willingness to self-report behavior (Maggia, et al., 2004; Reinert & Allen, 2007), particularly when there may be perceived consequences. Therefore, confidentiality issues will be stressed during informed consent which will include the description of a federal Certificate of Confidentiality which provides an additional layer of human subject protection. Participants will also be assured that their screening results, HIV test results, study participation, and study data will not be made available to any representative of the jail or criminal justice system. Jail officials and administrators will not be informed of participants who participate in the screening, eligibility data, or refusals in order to protect participant confidentiality.

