- It is possible, that a study participant may experience anxiety, emotional distress, or other negative reactions due to the content of the interview questions, HIV testing, and/or intervention. Based on our experiences working with this population, such occurrences are rare. However, with the participant's permission, they will be referred to the medical staff at the jail for additional help and support related to psychological distress. Participants will also be given a referral sheet for additional mental health and substance abuse services in the community.
10. **Safety Precautions:** All interviews and intervention sessions will take place in private, confidential office setting. All data collected will be kept in password protected files on a secure server and under lock/key. Clients will also be reminded that their legal status will not be altered based on their participation in the study. As an additional safeguard to ensure protection of client confidentiality, a Certificate of Confidentiality will be obtained from DHHS following IRB approval.
11. **Benefit vs. Risk:** The potential benefits of the proposed study are significant. First, all respondents will have equal opportunity to be screened as assessed for substance abuse risk. Second, for participants randomized into

the MI-HIV condition, there will be additional jail-based intervention for dealing with substance abuse, HIV risk, and other potential barriers that might increase the risk to a participant's recovery. Third, there will be significant potential benefits to science because the study will provide important information about the feasibility of delivering services to women in rural areas who otherwise face enormous challenges to service utilization. The proposed study may also provide information which can be used to improve substance abuse programs and services for rural women as well as reduce drug use, related risk behavior, and drug-related crime. Fourth, the project will generate important information related to rural female drug users' treatment needs, access to services, and barriers to care, providing the foundation for a future real-world interventions.

12. **Available Alternative Treatment(s):** There are no alternatives to participation in this evaluation project except not participating.

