19. **Research Involving Non-English Speaking Subjects or Subjects from a Foreign Culture:** The target population is almost entirely English-speaking. Due to the commitment of delivering a manualized intervention required in this study, any non-English speaking participants will not be eligible for participation.

20. **HIV/AIDS Research:** HIV/HCV testing procedures are covered under #7 Research Procedures. Testing procedures will be using FDA and CDC approved for ORAQUICK Advance® HIV and HCV Rapid Testing. Testing of subjects will be conducted on a voluntary basis at all interview contacts. As such, none of the subjects will be coerced in any way to submit to testing. As shown on the consent form, consent to test is separate, and participants may be able to participate in the larger study without consenting to the HIV/HCV testing procedures. They will also be asked to consent for release of any positive HIV screen to the state Department for Public Health in Frankfort knowing that a HIV care coordinator may be contacting them for additional follow-up. In addition: (a) subjects who refuse HIV/HCV testing at baseline or follow up interviews will nevertheless be retained in the sample; (b) HIV/HCV test results collected at the initial and follow up assessment points will be used for research purposes only and will not be made available to correctional or treatment program authorities; (c) all HIV/HCV testing will include pre- and post-test counseling following Centers for Disease Control and Prevention (CDC) protocols; (d) subjects testing positive for HIV/HCV infection will be retained in the study; and, (d) subjects testing positive for HIV/HCV infection will be given referral information as to the appropriate community resources for counseling and treatment, and assisted in contacting these agencies if they so desire it.
21. **PI-Sponsored FDA-Regulated Research:** N/A

References

- [ADAM] Arrestee Drug Abuse Monitoring (2003). Annual Report 2000. US Department of Justice/National Institute of Justice: Office of Justice Programs. Retrieved August 12, 2011 from <http://www.ncjrs.gov/pdffiles1/nij/193013.pdf>.

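### The protocol does not say who makes the jail medical referral after a positive test; a referral made by study staff without permission would break the assurance that HIV results and study participation are kept from the jail

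*Protocol*

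**What the plan says.** Section 7 (Research Procedures, HIV/HCV Testing) gives three referral routes after a positive result.

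- **Outside agencies:** "if the respondent wishes, referrals will be made to appropriate agencies".
- **Jail medical staff:** women with a positive test during their jail stay "will be referred to the medical staff at the jail for additional services, but it is their option to follow through on services" while incarcerated.
- **Community services:** women who do not want care inside the jail "will be offered referrals to community-based services once released".

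Section 9 (Potential Risks) covers distress caused by the interview, the HIV testing or the intervention. It makes referral conditional on the participant's "permission, they will be referred to the medical staff at the jail for additional help and support related to psychological distress".

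Three sections restrict what may reach the jail.

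- **Section 9:** participants are assured that "HIV test results, study participation, and study data will not be made available to any representative of the jail or criminal justice system".
- **Section 6 (Informed Consent Process):** "No individual or identifiable data collected as part of a study protocol will be made available to any criminal justice authority including jail".
- **Section 20 (HIV/AIDS Research):** HIV/HCV results "will be used for research purposes only and will not be made available to correctional or treatment program authorities".

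Section 20 also says that women who test positive receive referral information and are "assisted in contacting these agencies if they so desire it".

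**The concern.** The option in the section 7 jail sentence attaches to using the services, not to being referred. If study staff contact the jail's medical staff because of a positive test, the result and the woman's participation are known to the jail from that moment, and her later choice about services protects nothing. The protocol asks permission before contacting the same staff about distress, yet states no such step for an HIV or HCV result, which is more sensitive. The people at risk are incarcerated women who were promised that this information would be kept from the jail. A disclosure could not be undone.

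**Working it through.** The point rests on no figure in the plan, so there is nothing to recompute. The check is a comparison of the text.

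1. **Is the section 7 jail referral conditional?** Not in its own sentence. The wish condition stands in an earlier sentence of the same paragraph and governs referrals to appropriate agencies. The protocol does not say whether jail medical staff count as such an agency.

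2. **Is a permission condition used elsewhere for the same recipient?** Yes, in section 9 for distress, with the same verb. Asking permission has little purpose if being referred only means being told where to go, so the section 9 wording suggests that staff make the contact.

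3. **Who are the jail medical staff?** Section 8 (Resources) says that each jail provides medical services and that these can take referrals connected with HIV/HCV testing. Treating them as representatives of the jail is a fair reading, and a referral that they receive from study staff is at least as natural as one that the woman starts.

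4. **Which assurances reach them?** Section 9 does so most plainly, since it excludes every jail representative. It names HIV results; for an HCV result, its cover of participation and study data still applies. Section 20 covers HIV and HCV results expressly. But sections 6 and 20 speak of authorities, and applying that word to medical staff takes a small inference. They point the same way with less force.

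5. **Is there an exception?** None of the three assurances has a medical one. The only release of a positive result for which the protocol describes consent is that of an HIV screen to the state health department.

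6. **The two readings compared:**

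| Who makes the jail referral | What the jail learns from study staff | Consistent with section 9? |
|---|---|---|
| Study staff, without permission | Participation and the positive result | No |
| The woman herself, using information given to her | Nothing | Yes |

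Section 7 does not choose between the rows. Section 20 shows that the protocol can describe the second one clearly: information goes to the woman, and staff help with contact only if she wants it.

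**The case against.** The strongest reply is that this is an ambiguity and not a contradiction, and that the context favours the harmless reading. The paragraph first makes agency referrals depend on the woman's wish. The jail sentence leaves follow-through to her, and the next sentence provides for women who do not want jail care. Shortly before, section 7 says that women are told their results stay confidential. Section 17 bars anyone outside the study staff from reviewing identifying data. Trained, certified counselors who read the whole protocol would be unlikely to take one passive verb as an order to disclose. The distress referral is also a different event, where staff may need to seek help directly. Finally, the consent form and the counseling protocols are not visible and may settle the matter.

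Much of this stands. A reader might infer that the protocol plans to pass positive results to the jail. It does not: no section says so, and self-referral fits every section. A reader might also infer that three assurances are breached alike; only section 9 plainly reaches jail medical staff. Nor would it help to count how many other referral instructions are conditional, because classing this one as unconditional already assumes the disputed reading.

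What does not stand is that the context settles the question. Offering community referral to women who decline jail care supplies another service; it does not say that their wish is sought before the jail referral. Sections 8 and 9 make a referral by study staff at least as natural. A consent form that covered the point would still leave the protocol's own text unresolved.

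**Conclusion.** The point holds in a limited form. Section 7 states the jail referral without a permission condition and does not say who makes it. If study staff make it without permission, they cannot also keep the section 9 assurance. If the woman refers herself, there is no conflict. The conclusion assumes that jail medical staff are representatives of the jail, which section 8 supports but does not state in those words.

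This is a minor participant-protection correction. It touches only women who accept the voluntary test and test positive in jail. It has no bearing on randomisation, endpoints, sample size or inference. It merits correction because the possible harm is irreversible and the change is one clause.

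**What to change.** Change the jail sentence in section 7 in one of two ways.

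- **Preferred:** state that a woman who tests positive is given referral information so that she may approach the jail medical staff herself. Every assurance then stays as written.
- **Alternative:** state that study staff refer her only with her documented permission, as section 9 does for distress. The assurances then need a short exception for a referral that she has permitted in writing, mainly in section 9. The distress referral, which has no such exception now, would be covered too.

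The first option is better because it does not qualify absolute promises made to prisoners. Either way, check that the consent form agrees.

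The cost is ethics board review of the wording. Some women may decline the jail referral, but section 7 already offers them community referral after release. Sample, schedule and analysis are unchanged.
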